## 6.17. Interim Analyses and Data Monitoring

An interim database lock and unblinding will occur, and the analysis will be performed at the time (that is, a cut-off date) the last patient completes Visit 15 (Week 52) or ETV. This interim database lock will include all data collected by the cut-off date including follow-up data from patients who have begun the Post-Study Follow-Up Period (Period 3). Because the study will still be ongoing for the Post-Study Follow-Up Period at the time of this database lock, the analysis will be referred to as an interim analysis. The analyses from the Week 52 lock will be treated as a primary analysis because all primary and major secondary study objectives will be assessed at this time.

Unblinding details are specified in the blinding/unblinding plan.

## 6.18. Planned Exploratory Analyses

- To assess the psychometric properties (including reliability, validity, and responsiveness) of the ASAS HI in the ITT Population
- To assess the psychometric properties (including reliability, validity, and responsiveness) of the SF-36 components and norm-based domain scores in the ITT Population.
- To explore the impact of each ixekizumab regimen on change from baseline in measures of health utility (EQ-5D); and healthcare resource utilization in the double-blind dosing period in the ITT Population.

### 6.18.1. Psychometric Properties of ASAS HI

Unless stated otherwise, the analysis population of the psychometric properties of ASAS HI is ITT Population. The psychometric properties of the ASAS HI will be evaluated per the following analyses:

- Descriptive statistics for ASAS HI including sample size, mean, median, SD, min, max, % min, % max and % missing, will be provided for the baseline and at Week 16. The number and percentage of ASAS HI of 0,1,..., and 17 will also be summarized at baseline and at Week 16. Number and percentage of patients with each ASAS HI item score will also be summarized.
- Convergent and discriminant validity will be assessed by Pearson correlation and Spearman rank-based correlation coefficient at baseline and at Week 16 between ASAS HI and other clinical assessments, including BASFI, BASDAI, Spinal Pain (BASDAI item 2), EQ-5D UK Index, SF-36 MCS, SF-36 PCS, Patient Global Assessment of disease activity and fatigue NRS. Cohen's conventions (any absolute correlation at or of value greater than 0.5 is large, 0.3 to <0.5 is moderate, 0.1 to <0.3 is small, and anything smaller than 0.1 is insubstantial) will be used to interpret the results. It is hypothesized there will be small to moderate correlations at baseline and moderate to large correlations at Week 16 between the ASAS HI and all clinical measures, except for CRP. The correlations between ASAS HI and CRP at baseline and Week 16 are hypothesized to be small to moderate.

- Known groups validity of ASAS HI will be evaluated using one-way ANOVA with Scheffe's correction for post-hoc pairwise comparison, in distinguishing ASAS HI scores at baseline and Week 16 (mBOCF) between subgroups defined on the basis of ASDAS category:  $ASDAS < 2.1$ ,  $2.1 \leq ASDAS \leq 3.5$  and  $ASDAS > 3.5$ . If the sample size for any ASDAS category is less than 10% of the total sample size, the ASDAS category will be collapsed with lower category.
- Responsiveness will be evaluated by the correlations of ASAS HI changes from baseline to Week 16 (mBOCF) with changes from baseline in other clinical assessments, including BASFI, BASDAI, ASDAS, and Patient Global Assessment of disease activity to Week 16 (mBOCF). Moderate to large correlations are hypothesized based on Cohens' conventions. Additionally, responsiveness will be evaluated using one-way ANCOVA comparing mean change in ASAS HI (mBOCF) between subgroups defined on the basis of (1) ASAS response status at Week 16: not achieving ASAS20; achieving ASAS20 but not ASAS40; and achieving ASAS40, and (2) BASDAI response status at Week 16 (NRI): BASDAI50 nonresponder and BASDAI50 responder, and (3) ASDAS disease activity:  $ASDAS < 1.3$ ,  $1.3 \leq ASDAS < 2.1$  and at  $ASDAS \geq 2.1$ , (4) ASDAS improvement  $< 1.1$ ,  $1.1 \leq ASDAS$  improvement  $< 2.0$  and  $2.0 \leq ASDAS$  improvement, after with and without controlling for baseline ASAS HI. Missing ASAS response status will be treated as not achieving ASAS20. It is hypothesized that an overall statistically significant difference will be observed ( $p < 0.05$ ) with at least one statistically significant subgroup comparisons.
- Test-retest reliability will be assessed in stable patients during the interval between screening and baseline assessment (the 2 assessments will be separated by 4 - 42 days). Stable patients will be defined as those with no more than  $\pm 1.5$  points difference in BASDAI ratings between screening and baseline. Intraclass correlation coefficients (ICCs) and change scores will be calculated between the initial and retest to evaluate test-retest reliability. An ICC of 0.70 is considered acceptable agreement (Nunnally and Bernstein 1994). The analysis population for test-retest reliability will be all patients with both screening and baseline assessments.
- Internal consistency of ASAS HI total score at baseline and at Week 16 will be evaluated using Cronbach's alpha. Inter-item correlation will be quantified using two metrics: simple agreement and Yule's Q coefficient.
- The responder definition of ASAS HI will be derived using both anchor-based and distribution-based methods. In the distribution-based method, 1.00 and 1.96 times the standard error of measurement (SEM) bears alignment with meaningful change over time (Wywich 2004) and are considered thresholds for minimal detectable change. The anchor-based method will utilize the empirical cumulative distribution function (eCDF) and probability density function (PDF) plots to explore the relationship between selected anchors, including ASAS40, ASAS20, BASDAI50, sPGA change of  $\leq -4$ ,  $-3$ ,  $-2$ ,  $-1$ ,  $0$ ,  $1$ ,  $2$ ,  $3$ , and  $\geq 4$  and  $ASDAS < 2.1$  response status at Week 16 (NRI) and the change in ASAS HI from baseline to Week 16 (mBOCF). The eCDF and PDF plots of the ASAS HI total score change from baseline to Week 16 using pooled sample will be provided, including sample sizes and median scores in each plot's legend.

- The empirical cumulative distribution function (eCDF) and probability density function (PDF) plots for change in ASAS HI from baseline to Week 16 (mBOCF) will be presented by treatment group (including placebo).

### **6.18.2. Psychometric Properties of SF-36 components and norm-based domain scores**

- Test-retest reliability will be assessed in stable patients during the interval between screening and baseline assessment (the 2 assessments will be separated by 4 - 42 days). Stable patients will be defined as those with no more than  $\pm 1.5$  point difference in BASDAI ratings between screening and baseline. Intraclass correlation coefficients (ICCs) and change scores will be calculated between the initial and retest to evaluate test-retest reliability. An ICC of 0.70 and above is considered acceptable agreement (Nunnally and Bernstein 1994). The analysis population for test-retest reliability will be all stable patients with both screening and baseline assessments.
- Known groups validity of SF-36 scores will be evaluated using one-way ANOVA with Scheffe's correction for post-hoc pairwise comparison at baseline and Week 16 (mBOCF) between subgroups defined on the basis of ASDAS category: ASDAS <2.1, ASDAS  $\leq 2.1$  to  $\leq 3.5$ , and ASDAS >3.5.
- Convergent and discriminant validity will be assessed by Pearson correlation and Spearman rank-based correlation coefficient at baseline and at Week 16 between SF-36 scores and other clinical assessments, including BASFI, BASDAI, Spinal Pain (BASDAI item 2), EQ-5D UK Index, Patient Global Assessment of disease activity, CRP, WPAI work productivity loss, WPAI activity impairment and fatigue NRS. Cohen's conventions (any absolute correlation at or value greater than 0.5 is large, 0.3 to <0.5 is moderate, 0.1 to <0.3 is small, and anything smaller than 0.1 is insubstantial) will be used to interpret the results. It is hypothesized there will be small to moderate correlations at baseline and moderate to large correlations at Week 16 between SF-36 and all clinical measures, except for CRP. The correlations between SF-36 and CRP at baseline and Week 16 are hypothesized to be small to moderate.
- Responsiveness will be evaluated by the correlations of SF-36 changes from baseline to Week 16 (mBOCF) with changes from baseline in other clinical assessments, including BASFI, BASDAI, ASDAS, and Patient Global Assessment to Week 16 (mBOCF). Moderate to large correlations are hypothesized based on Cohens' conventions. Additionally, responsiveness will be evaluated using one-way ANCOVA comparing mean change in SF-36 (mBOCF) between subgroups defined on the basis of (1) ASAS response status at Week 16: not achieving ASAS20; achieving ASAS20 but not ASAS40; and achieving ASAS40, and (2) BASDAI response status at Week 16 (NRI): BASDAI50 nonresponder and BASDAI50 responder, and (3) ASDAS disease activity: ASDAS <1.3, ASDAS  $\leq 1.3$  to <2.1, and at ASDAS  $\geq 2.1$ , (4) ASDAS improvement <1.1, ASDAS improvement  $\leq 1.1$  to <2.0, and  $2.0 \leq$  ASDAS improvement, after with and without controlling for baseline SF-36 score. Missing ASAS response status will be

treated as not achieving ASAS20. It is hypothesized that an overall statistically significant difference will be observed ( $p < 0.05$ ) with at least one statistically significant subgroup comparisons.

The anchor-based eCDF and PDF plots of the SF-36 change scores from baseline to week 16 using pooled sample will be provided for anchor ASAS40, ASAS20, BASDAI50, sPGA change of  $\leq -4$ ,  $-3$ ,  $-2$ ,  $-1$ ,  $0$ ,  $1$ ,  $2$ ,  $3$ , and  $\geq 4$  and ASDAS  $< 2.1$  response status at Week 16 (NRI) and change in SF-36 score from baseline to Week 16 (mBOCF), including sample sizes and median scores in each plot's legend. The eCDF and PDF plots of the SF-36 change scores from baseline to week 16 using pooled sample will be provided, including sample sizes and median scores in each plot's legend.

### 6.18.3. Association Between Clinical Outcomes and Health Outcomes/Quality-of-Life Measures

The objective of the following analysis is to determine whether greater improvement in clinical outcomes from baseline to Week 16, as assessed by categorized ASAS, BASDAI, and ASDAS is associated with larger improvement from baseline to Week 16 in the following continuous health outcome measurements: ASAS HI, Fatigue NRS, SF-36 PCS, SF-36 MCS, and WPAI-SpA. Association between clinical outcomes and categorical health outcomes will also be investigated.

Clinical outcomes will be categorized according to [Table RHBX.6.13](#).

**Table RHBX.6.13. Categorization of Clinical Outcomes**

Categorization	Clinical Outcomes at Week 16 a			
	ASAS	BASDAI	ASDAS static	ASDAS improvement
(1)	ASAS40 Nonresponder	BASDAI50 Nonresponder	ASDAS very high disease (ASDAS > 3.5)	$\Delta$ ASDAS < 1.1
(2)	ASAS40 Responder	BASDAI50 Responder	ASDAS high disease ( $2.1 \leq$ ASDAS $\leq 3.5$ )	$1.1 \leq \Delta$ ASDAS < 2.0
(3)			ASDAS inactive/moderate disease activity (ASDAS < 2.1)	$2.0 \leq \Delta$ ASDAS

Abbreviations: ASAS = Assessment of Spondyloarthritis International Society; ASDAS = Ankylosing Spondylitis Disease Activity Score; BASDAI = Bath Ankylosing Spondylitis Disease Activity Index.

a Above association analyses between clinical outcomes and health outcomes/quality-of-life measures may be conducted at Week 52 as well.

Missing categorical clinical outcomes and continuous health outcomes at Week 16 will be imputed by NRI and mBOCF methodology described in Sections 6.3.1 and 6.3.2, respectively. Missing categorical health outcomes will also be imputed using NRI method as described in Section 6.3.1.

The association analysis will be performed using the ITT Population with all treatment groups combined and the ITT Population with total ixekizumab groups.

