## 4. Study Design

### 4.1. Overview of Study Design

Study IIF-MC-RHBX (RHBX) is a Phase 3, multicenter, randomized, double-blind, placebo-controlled, parallel-group, outpatient study examining the efficacy and safety of 2 ixekizumab treatment regimens (80 mg Q2W and 80 mg Q4W SC) as compared to placebo SC in patients with active nonrad-axSpA who are bDMARD-naïve, during a double-blind, 52-week treatment period (Period 2).

[Figure RHBX.1](#) illustrates the study design. Within the active treatment groups, half the patients will be given a 160-mg starting dose and the other half will be given an 80-mg starting dose. All treatment groups and administration of the investigational product are described in [Section 6.1](#), and the Study Drug Administration Log is described in [Section 6.2.1](#).

All procedures to be conducted during the study, including timing of all procedures, are indicated in the Schedule of Activities ([Appendix 2](#)). Selected study procedures are to be performed before administration of the investigational product, as applicable.

For each patient, x-rays and magnetic resonance imaging (MRIs) will be collected according to [Section 8.1.2.21.1](#) and the Schedule of Activities ([Appendix 2](#)).

[Appendix 3](#) lists the specific laboratory tests that will be performed for this study. At or after Week 16, patients who are deemed inadequate responders may receive rescue therapies as described in [Section 6.1.1](#). Patients discontinuing study treatment after Week 16 are to remain in the study and follow the regular visit schedule.

[figure not shown]
Patients who have taken at least 1 study dose and who discontinue study treatment prior to Week 16 or study participation (regardless of timing) are to complete an early termination visit (ETV) and enter into post-study follow-up for at least 12 weeks after the ETV date or the last regularly scheduled visit. Patients whose ETV or last regularly scheduled visit is longer than 12 weeks after their last investigational study medication dose are not required to enter into the Post-Study Follow-Up Period (Period 3). For the management of patient safety, patients are to be monitored through the Post-Study Follow-Up Period as indicated on the Schedule of Activities ([Appendix 2](#)).

Patients who complete Study RHBX may be eligible to enroll into a long-term extension study (Study IIF-MC-RHBY [RHBY]) for up to 2 additional years.

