### 6.3.1. Nonresponder Imputation

Analysis of categorical efficacy and health outcome variables will be assessed using a nonresponder imputation (NRI) method. Patients will be considered nonresponders for the NRI analysis if they do not meet the clinical response criteria or have missing clinical response data at the primary analysis time points. All nonresponders at Week 16 (Visit 8), as well as all patients who discontinue study treatment at any time prior to Week 16 for any reason, will be defined as nonresponders for the NRI analysis at Week 16. Similarly, all nonresponders at Week 52 (Visit 15), as well as patients who discontinue study treatment at any time prior to Week 52 for any reason, will be defined as nonresponders for the NRI analysis at Week 52. Patients who are deemed as inadequate responders by the investigator on or after Week 16 but remain on initially assigned blinded study treatment and only have modifications in concomitant medications will not influence whether or not a patient would be considered a nonresponder. Patients who stopped originally assigned blinded study treatment and use rescue ixekizumab 80 mg Q2W will be analyzed as nonresponders for the Week 52 analysis. They will be considered as nonresponders after the time of initiation of biologic rescue of ixekizumab 80 mg Q2W.

Randomized patients without at least 1 postbaseline observation will also be defined as nonresponders for the NRI analysis.

The NRI may be applied at any time point specified for analysis.

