Ankylosing Spondylitis Disease Activity Score (ASDAS)	The ASDAS is a composite index to assess disease activity in AS (Machado et al. 2011a, 2011b; Zochling 2011). The parameters used for the ASDAS (with CRP as acute phase reactant): 1) Total back pain (BASDAI	ASDAS crp	ASDAS crp (Sieper et al. 2009, pg 41): $0.121 \times \text{total back pain} + 0.110 \times \text{patient global} + 0.073 \times \text{peripheral pain/swelling} + 0.058 \times \text{duration of morning stiffness} + 0.579 \times \text{Ln}(\text{CRP}+1)$ (Machado et al. 2015). C-reactive protein is in mg/liter, the range of other variables is from 0 to 10; Ln represents the natural logarithm.	Missing if any of the components is missing. If CRP <2 mg/L or below the limit of detection, then use 2 mg/L in the calculation (Machado et al. 2015).

Measure	Description	Variable	Derivation / Comment	Imputation Approach if with Missing Components
	Q2) 2) Patient global 3) Peripheral pain/swelling (BASDAI Q3) 4) Duration of morning stiffness (BASDAI Q6) 5) CRP in mg/L	ASDAS crp change from baseline - major secondary outcome	Calculated as: observed ASDAS – baseline ASDAS	Missing if baseline or observed value is missing
		ASDAS Disease Activity States	Four (4) disease activity states have been defined by ASAS consensus (Machado et al. 2011c): 
 
• ASDAS <1.3 defines inactive disease
 
• <math>1.3 \leq \text{ASDAS} < 2.1</math> defines low disease activity
 
• <math>2.1 \leq \text{ASDAS} \leq 3.5</math> defines high disease activity
 
• ASDAS > 3.5 defines very high disease activity
 
	Set the disease activity state to worst state (i.e. very high) if observed ASDAS score is missing
		ASDAS <2.1 Major secondary outcome	Defined as ASDAS < 2.1 (low or inactive disease activity)	
		Clinical important improvement	Defined as at least 1.1 unit change in ASDAS from baseline	Missing if baseline or observed ASDAS score is missing
		Major improvement	Defined as at least 2.0 unit change in ASDAS from baseline or reached the minimum of ASDAS score (0.6361) at postbaseline visit	

Measure	Description	Variable	Derivation / Comment	Imputation Approach if with Missing Components

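### In the categorical part of SAP 6.18.3, nonresponder imputation on both variables puts every early discontinuer in one concordant cell and inflates the association

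*SAP*

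**What the plan says.** SAP 6.18.3 asks whether larger clinical improvement to Week 16, categorised in Table RHBX.6.13 by ASAS40, BASDAI50, ASDAS state and ASDAS improvement, goes with larger improvement "in the following continuous health outcome measurements: ASAS HI, Fatigue NRS, SF-36 PCS, SF-36 MCS, and WPAI-SpA". It then adds: "Association between clinical outcomes and categorical health outcomes will also be investigated". For this addition it names no outcome, association measure or test. Elsewhere, Table RHBX.6.7 analyses two binary ASAS HI outcomes with NRI.

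On missing data, the text under Table RHBX.6.13 says: "Missing categorical clinical outcomes and continuous health outcomes at Week 16 will be imputed by NRI and mBOCF methodology". For the added part it says: "Missing categorical health outcomes will also be imputed using NRI method as described in Section 6.3.1". Under SAP 6.3.1, a missing response counts as nonresponse, and so does any stop of study treatment before the time point, whatever was measured. For ASDAS states, Table RHBX.6.4 has: "Set the disease activity state to worst state (i.e. very high) if observed ASDAS score is missing".

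The analysis is run in the ITT population with all arms combined and again in the combined ixekizumab groups. Week 16 is the planned time point. A footnote to Table RHBX.6.13 adds: "Above association analyses between clinical outcomes and health outcomes/quality-of-life measures may be conducted at Week 52 as well". For Week 52, SAP 6.3.1 states that patients who leave their assigned treatment and "use rescue ixekizumab 80 mg Q2W will be analyzed as nonresponders for the Week 52 analysis". Protocol 4.1 says: "Patients discontinuing study treatment after Week 16 are to remain in the study and follow the regular visit schedule". Section 6.18.3 plans no analysis of observed pairs.

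**The concern.** NRI is normally defended as cautious, because counting dropouts as failures makes it harder to credit a drug with benefit. That defence needs a comparison between arms. Here the arms are pooled and the question is how two measures move together within a patient. When both are set to nonresponse by the same event, the patient is a concordant pair because the rule says so.

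The reported association then depends partly on how many patients stopped treatment. A result offered as evidence that clinical response carries patient-reported benefit would mix measured concordance with imposed concordance, and 6.18.3 gives the reader no means of separating them.

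**Working it through.** **Inputs.**
- Clinical response p: SAP 5.2 assumes ASAS40 at Week 16 of 46% on Q2W and 18% on placebo. If Q4W equals Q2W (an assumption), the pooled rate is (46 + 46 + 18)/3 = 36.7%.
- Health-outcome response q: not in the documents. Assumed 0.40, range 0.30 to 0.50.
- Share m imputed on both variables: not in the documents. Assumed 5% and 10% for Week 16, and 30% for a Week 52 version that includes rescue.
- N: about 300 pooled (SAP 5.2).

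**The plan's own figure.** Section 6.18.3 states none. The power statement that supplies p reproduces: exact enumeration of the two-sided Fisher test gives 98.8%, against the stated approximately 98%.

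**Effect of the rule on a 2x2 table.** Among observed patients let the cell proportions be a (both respond), b and c (discordant) and d (neither responds). The rule shrinks all four by (1 − m) and adds m to the last. So

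OR after NRI = a[(1 − m)d + m] / [(1 − m)bc] = true OR × {1 + m/[(1 − m)d]}.

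**No true association.** True OR = 1 and d = (1 − p)(1 − q) = 0.633 × 0.60 = 0.3798.
- m = 5%: 1 + 0.05/(0.95 × 0.3798) = 1.14
- m = 10%: 1 + 0.10/(0.90 × 0.3798) = 1.29
- m = 30%: 1 + 0.30/(0.70 × 0.3798) = 2.13

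Over p from 0.367 to 0.46 and q from 0.30 to 0.50, the ranges are 1.12 to 1.19, 1.25 to 1.41 and 1.97 to 2.59. If 0.367 and 0.40 are instead overall rates after NRI, the odds ratio is 1.34 at 10% and 3.10 at 30%. With an assumed chi-square test at the 0.05 level and N = 300, the chance of rejection is 8% at m = 5% and 17% at m = 10%. Observed pairs give an odds ratio of 1.00 and 5%.

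**A true association.** With OR = 5 and the same p and q, the cells are a = 0.2345, b = 0.1325, c = 0.1655, d = 0.4675.
- m = 5%: 5 × [1 + 0.05/(0.95 × 0.4675)] = 5.6
- m = 10%: 5 × [1 + 0.10/(0.90 × 0.4675)] = 6.2
- m = 30%: 5 × [1 + 0.30/(0.70 × 0.4675)] = 9.6

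**Only the health outcome missing.** For a patient still on treatment, the clinical value is kept. If a share u lacks the health outcome, the cells become a(1 − u), b + au, c(1 − u), d + cu. The true OR of 5 falls to 4.7 at u = 5% and 4.4 at u = 10%, so this bias runs the other way.

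**Continuous health outcomes.** The clinical member is set to nonresponse and the health outcome follows mBOCF (SAP 6.3.2). After an AE discontinuation the change is 0. With no true association, an assumed mean change of 7 and SD of 8, and a share f of discontinuations due to AE, the spurious difference is 7 × mf/[1 − (1 − m)p]. At m = 10% the denominator is 1 − 0.90 × 0.367 = 0.6697, and f = 25%, 50% and 100% give 0.26, 0.52 and 1.05 points; simulation gave 0.27, 0.53 and 1.03. After other discontinuations the last value is kept under a nonresponder label, which weakens a real difference. If the carried value equals the true one, a difference of 8 with 10% such dropouts becomes 8 × [1 − 0.10 × 0.367/0.6697] = 7.6.

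**Timing of rescue.** Protocol 6.8.2 places treatment modification after the Week 16 assessments, and SAP 6.3.1 makes a rescued patient a nonresponder only once rescue has started. Rescue therefore adds nothing to m at Week 16.

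**The case against.** The strongest reply is that this is a one-sentence addition to an exploratory analysis. The named outcomes are continuous, and there the distortion is small against an SD of 8 and mixed in direction. Independence is also an unrealistic null: SAP 6.18.1 and 6.18.2 themselves hypothesise moderate to large correlations of ASAS HI and SF-36 with clinical measures. Going from 5 to 5.6 or 6.2 would not change a conclusion. Those two sections also already correlate changes with mBOCF on both members. Restricting to observed pairs has its own cost: patients who stop before Week 16 go to an early termination visit and follow-up, so they drop out of the analysis, and those who left for lack of effect may truly have been nonresponders on both. Finally, using data after rescue departs from SAP 6.1.1 and 6.1.2.1.

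Most of this stands, and it limits the point. It does not remove it. The 6.18.1 and 6.18.2 correlations do not cover categorical health outcomes, Fatigue NRS or WPAI-SpA, and 6.18.3 has no check of its own.

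A reader might infer more: that all of 6.18.3 uses NRI on both sides, that every missing or rescued patient becomes a concordant pair, and that the bias always favours association. The documents do not support this. The named outcomes use mBOCF, a patient on treatment with one variable missing can be discordant, and rescue does not reach Week 16.

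**Conclusion.** The point holds for the categorical-by-categorical part of SAP 6.18.3. Patients who stop study treatment before the time point, or who miss both variables, are concordant nonresponders by rule, and this component inflates the association. At Week 16 the effect is modest if few patients are imputed. It could be large in a Week 52 version, an odds ratio of about 2.1 under independence at an assumed 30%, but that version is optional.

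The figures rest on assumed values of m and q, on Q4W responding like Q2W, and on a binary pair; the two ASDAS variables in Table RHBX.6.13 have three levels. The better guide is inflation of a real association. That the analysis would report an association where none exists is a further reading, and it needs an independence that the SAP does not expect. Continuous pairs are affected less, mainly through AE discontinuations set to zero change. The analysis lies outside the multiplicity scheme in SAP 6.5. Severity: minor.

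**What to change.** In SAP 6.18.3:
- Report the association in patients with both variables observed at the visit, as the main result or at least beside the NRI result, and state how many pairs were fixed by imputation.
- For imputed continuous pairs, derive the clinical category from component scores carried forward by the same mBOCF rule as the health outcome, so that both members rest on one assumption.
- If the Week 52 version is run, show observed post-rescue pairs as a separately labelled analysis, because ITT analyses in Period 2 otherwise use data only up to rescue.

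The cost is SAP wording and one analysis dataset. The downsides are fewer patients, possible selection from losing early discontinuers, and counts that no longer match the NRI tables. Showing both results side by side lets the reader judge the selection.
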